## **4 Aims of the trial**

### **4.1.1 Overall aim**

Prediction of short and long term outcome of treatment for squamous cell cancer (SCC) by monitoring tumour response during early treatment phases.

### **4.1.2 Specific aims**

- Correlate changes in imaging bio-markers to corresponding changes in tissue or blood bio-markers by repeated imaging and biopsies for better understanding of the image parameters.
- To correlate data from multiparametric imaging to specific outcome
- Validation of early bio-imaging predictors of tumour response and patient outcome.

## **4.2 End points**

### **4.2.1 Primary end point**

- Loco-regional control 2 years after completion of radiotherapy

### **4.2.2 Secondary end points**

- Loco-regional tumour control 8 (-2 - +4) weeks after completion of radiotherapy
- Patterns of failure
- Progression free survival at 2 years
- Overall survival at 2 and 5 years
- Changes in imaging and metabolic data
- Site specific toxicity at 12 months after completion of radiotherapy

[figure not shown]
## **5 Study design**

The study is prospective, multi-centre, non-randomised observational study for investigation and validation of imaging biomarkers for early treatment response. Patients are recruited with previously untreated SCCs aimed for radiotherapy with curative intent of the oral cavity, oropharynx, uterine cervix, oesophagus, anal canal or lung. Multimodal, functional imaging data are collected before and during the early phase of radiotherapy. In parallel to the imaging data, tumour biopsies and blood will be collected for molecular analyses that may provide explanatory information to the imaging information.

## 5.1 Study period

The inclusion period is calculated to be three to four years. The study ends five years after inclusion of the last patient.

## 6 Study flow chart

## 7 Overview of study assessments

Patients will be investigated by MR, PET and biopsy/FNAC (fine needle aspiration cytology) twice during the study period.

The first session of imaging will be performed within two weeks from planned start of radiotherapy (without reference to any other possible anticancer treatment (e.g. chemotherapy). In cases where MR and PET are not performed simultaneously they should be performed not more than one week apart. Tissue specimens should be obtained as soon as possible before imaging.

The tissue specimen for metabolomics analyses should be immediately frozen (within minutes from procedure!). Matching specimen for histological verification and future molecular biology studies should also be obtained and handled according to addendum.

The second assessment will be performed on Day 8 (+/-1) after start of radiotherapy (date of first radiation fraction is defined as Day 1). Adjustments of the timing for the second assessment will be determined by using pre-planned variable times for the first 20-30 patients in the pre-study. Thus, optimising the time interval for different sub-sites. In departments where MRI and PET can not be performed simultaneously, the MRI should be performed according to protocol. The PET assessment should be performed in close connection but not more than 24 h apart from MRI. The biopsy/FNAC should preferably be performed after imaging in order to avoid bleeding or edema blunting the imaging. It is recommended that the images produced are used as guidance for directing the biopsies at volumes assumed to contain active tumour tissue. If this is not practically

possible the biopsy/FNAC may be performed before imaging under the condition that the surgeon provides detailed description of the location of the biopsy in order to allow for correcting the results for possible artefacts in the vicinity of the biopsy.

For imaging sessions the patients shall be in therapy position wearing regular fixation devices for therapy. E.g. in the head and neck region this means that head coils etc may not be used and other coil arrangements with flexible coils will be predominant. In order for the patients to avoid higher degrees of discomfort the total time for the imaging procedure shall be planned to last not more than 30 minutes. This means that the number of protocols used for each imaging session must be carefully optimised. The first 20-30 patients will be the part of a pre-study where the usefulness of different protocols will be evaluated and the procedure optimised.

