**Radiotherapy and possible neo-adjuvant, concomitant or adjuvant therapy**

The standard treatment schedules according to clinical routines and decisions will be followed irrespective if the patient is taking part in the study or not. Specific information on all anticancer therapy (doses and timing) will be recorded for each patient. The observation will commence at start of radiotherapy irrespective when and how other supporting therapies are used.

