**Statistical methods**

To find potentially relevant patterns of response in the large amount of data for each patient, chemometric methods will be applied

To estimate the degree of agreement between predicted and observed response the Cohen's Kappa will be used.

Criteria for evaluation	Patients who have undergone per protocol imaging sessions before and during therapy
Planned sample size	412 patients
Analysis plan	The primary endpoint will be analysed when median follow up is two years.
Duration of the study	Three to four years inclusion, five year follow-up after inclusion of the last patient.

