## **8 Patient selection criteria**

### **8.1 Inclusion criteria**

1. Morphologically (pathology or cytology) verified, previously untreated SCCs of the oral cavity, oropharynx, uterine cervix, esophagus, anal canal or lung.
2. The patient should be planned for treatment with radiotherapy alone or in combination with concomitant medical therapy
3. The tumour shall be radiologically and/or visually identifiable and accessible for biopsy without the need for general anaesthesia or other major interventions
4. The patient must be at least 18 years of age, able to understand the given information and, leave a written informed consent to participate

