### 12.2 Statistical methods

Changes in imaging parameters and metabolomics patterns will be used for statistical inference. We also intend to apply multivariate data reduction and texture analyses techniques on multi-dimensional parametric images from the study population. In this part of the project a close collaboration is planned with the project of [name]. All data will be stored in communicating databases for future re-analyses when long-term follow-up data is available and new methods for multiparametric analyses become available. Contrary to many studies that result in "promising results" we aim to bring preliminary findings to a higher level of validation and thus prepare for large scale clinical studies. In

the clinical data sampling procedures a pre-determined fraction of the patients will be randomised and stored separately for hypothesis validation.

Survival endpoints will be compared by Cox regression stratified for tumor site and corrected for all other covariates used in the minimization algorithm – i.e. a multivariate Cox regression will be applied with tumour sites as strata as covariates

The primary analysis will be based on the intention-to-treat analysis set. Every effort will be made to collect survival data on subjects, including subjects withdrawn from treatment for any reason, who are eligible to participate in the study and who have not withdrawn consent for survival data collection. OS is defined for each patient as the time between radiotherapy start date and death. If a patient has not expired, the patient will be censored at the time of last contact (last known alive date).

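### The protocol does not settle whether patients may have had systemic therapy before the baseline scan, and its kappa analyses would pool their change scores with those from an untreated baseline

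*Protocol*

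**What the plan says.** **Who enters.** Protocol section 8.1, like the synopsis, asks for untreated disease: "Morphologically (pathology or cytology) verified, previously untreated SCCs of the oral cavity, oropharynx, uterine cervix, esophagus, anal canal or lung". The next criterion reads "The patient should be planned for treatment with radiotherapy alone or in combination with concomitant medical therapy". Neo-adjuvant therapy is not named.

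**What other therapy is foreseen.** The synopsis has a paragraph on radiotherapy and "possible neo-adjuvant, concomitant or adjuvant therapy". It adds: "The observation will commence at start of radiotherapy irrespective when and how other supporting therapies are used". The same paragraph says that doses and timing of all anticancer therapy are recorded.

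**When the scans are done.** Section 7 places the first imaging session within two weeks of the planned start of radiotherapy, "without reference to any other possible anticancer treatment (e.g. chemotherapy". For the second session: "The second assessment will be performed on Day 8 (+/-1) after start of radiotherapy". That day can be adjusted after the pilot.

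**How the scans are used.** Section 12.2: "Changes in imaging parameters and metabolomics patterns will be used for statistical inference". The synopsis: "To estimate the degree of agreement between predicted and observed response the Cohen's Kappa will be used". Under section 12.1, lung and head and neck are analysed separately and also together with all other cases. The third group is mainly analysed within the aggregate. Section 12.4 draws one patient in four at random for hypothesis generation and keeps the rest for validation. No passage separates patients by therapy given before the baseline scan. The one adjustment described is a Cox model for survival endpoints, stratified by tumour site.

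**The concern.** The study's central predictor is an early change. Section 3.1 argues for studying changes soon after therapy begins, and the synopsis counts as evaluable those patients imaged both before and during therapy. For a patient who goes straight to radiotherapy, the first session is a true pre-treatment scan. For a patient who has had induction chemotherapy it need not be, because part of the response may already have taken place. The later change could then be small in a patient who goes on to do well.

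If both kinds of patient are enrolled, one variable carries two meanings inside each kappa. Agreement could be diluted to a degree that varies with tumour site and local practice. A disappointing kappa would then be harder to attribute to the marker itself. The Cox model does not help here, because it concerns survival endpoints and not agreement.

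The eligibility text leaves room for centres to differ. One centre could read the criteria as excluding induction therapy. Another could read the synopsis and section 7 as allowing it.

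**Working it through.** **1. The passages side by side.**

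| Place | What it implies for therapy before the baseline scan |
|---|---|
| Section 8.1, criteria 1 and 2 | Untreated tumour; radiotherapy alone or with concomitant therapy; earlier therapy not mentioned |
| Synopsis, paragraph on radiotherapy and other therapy | Neo-adjuvant therapy is possible; observation starts at radiotherapy regardless |
| Section 7 | First session timed to radiotherapy only, whatever chemotherapy is given |
| Sections 12.1, 12.2 and 12.4 | Change is the predictor; analysis by site and aggregated; no split by earlier therapy |

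The first row and the next two do not fit together without an added rule. The last row shows that nothing described in the analysis separates the patients concerned.

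**2. The plan's own sample size.** Section 12.1 gives 63 or 80 patients for kappa 0.4 against 0.7 with 90% power, at 50% or 20% responders. The significance level is not stated. I used the large-sample variance of kappa with equal marginals, V(k) = (1-k)[(1-k)(1-2k) + k(2-k)/(2p(1-p))]. At p = 0.5, V(0.4) = 0.84 and V(0.7) = 0.51. With one-sided 5%:

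n = [(1.645 × √0.84 + 1.282 × √0.51) / 0.3]² = 65.2, so 66.

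At p = 0.2 the same formula gives 101. One-sided 5% with predicted and observed response rates 10 points apart gives about 63 and 81, but that input is inferred. I therefore do not call the stated figures wrong. The present point does not depend on them.

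**3. Reference power at the chosen n = 70.** With 50% responders, one-sided 5% and kappa 0.70:

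z = (0.3 × √70 - 1.645 × √0.84) / √0.51 = (2.510 - 1.508) / 0.714 = 1.40, so power is 92%.

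**4. Illustration of dilution.** Every input in this step is assumed; none is in the protocol.

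- Mean change is -40% in responders and -15% in non-responders. The cut-off is the midpoint, -27.5%.
- The SD is set so that 85% are classified correctly: 12.5 / 1.036 = 12.06. With 50% responders, kappa = 2 × 0.85 - 1 = 0.70.
- In pretreated patients both means shrink by 30% or by 70%. The cut-off stays the same.

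Among pretreated patients:

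- 30% shrinkage (means -28 and -10.5): responders correct Φ(0.5/12.06) = 0.517; non-responders correct Φ(17/12.06) = 0.921; kappa = 0.517 + 0.921 - 1 = 0.437 before rounding.
- 70% shrinkage (means -12 and -4.5): responders correct Φ(-15.5/12.06) = 0.099; non-responders correct Φ(23/12.06) = 0.972; kappa = 0.071.

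Pooled kappa = (1 - f) × 0.70 + f × (kappa in pretreated), where f is the pretreated share:

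| f | Pooled kappa, 30% shrinkage | Pooled kappa, 70% shrinkage | Power at n = 70 |
|---|---|---|---|
| 0 | 0.70 | 0.70 | 92% |
| 10% | 0.630 + 0.044 = 0.67 | 0.630 + 0.007 = 0.64 | 86% to 73% |
| 20% | 0.560 + 0.087 = 0.65 | 0.560 + 0.014 = 0.57 | 77% to 48% |

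**5. A second assumed model.** Set kappa at 0.4 in pretreated patients and 0.7 in the others. Pooled kappa is then 0.67 at f = 10% and 0.64 at f = 20%, with power 84% and 74%. If kappa is the same in both kinds of patient, nothing is lost.

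**6. What restriction would cost.** If 20% are pretreated, 80% of 70 is 56 patients. With kappa 0.70, z = (0.3 × √56 - 1.508) / 0.714 = 1.03, so power is about 85%. If 30% are pretreated, n = 49 and power is about 80%.

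**The case against.** The best defence is that the baseline rule is a deliberate and openly stated choice. The study concerns response to radiotherapy. The change from shortly before radiotherapy to about Day 8 has the same operational definition in every patient. A scan before induction therapy would mix two treatment effects and lengthen the interval. This stands: anchoring to radiotherapy is not an error in itself.

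A reader might infer that the protocol admits patients whom its own criteria forbid. The text does not go that far. Criterion 1 does not say at what moment the tumour must be untreated, so a patient enrolled before induction could meet it. Criterion 2 does not expressly bar earlier therapy. The conflict is one of wording that needs reconciling.

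A reader might also infer that a shared cut-off will misclassify pretreated responders. No single cut-off appears in the protocol, which describes multivariate and chemometric methods. Hypothesis-generation patients are drawn at random, so the predictors would be developed on the same kind of case mix as the one used for validation. The cut-off belongs to the illustration only.

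Finally, splitting by earlier therapy is detail that an analysis plan may hold, and the dates needed are recorded. That answers much of the analysis concern. It does not settle who is eligible, which only the protocol can do.

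**Conclusion.** The point holds as an unresolved inconsistency with a possible effect on the main predictor. The eligibility criteria and the passages on neo-adjuvant therapy and baseline timing need to be reconciled. If patients with earlier systemic therapy are enrolled, the described kappa analyses would pool two kinds of change score.

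The size cannot be derived from the documents, which give neither the pretreated share nor the marker's performance in those patients. Under the assumed single cut-off, with 50% responders, one-sided 5%, n = 70 and 30-70% shrinkage, kappa falls from 0.70 to 0.67-0.64 at 10% pretreated and to 0.65-0.57 at 20%. It does not fall if no one is pretreated or if the marker works equally well in everyone.

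Two stronger conclusions are not supported. One is that a failed validation would be uninterpretable; the recorded treatment dates would still allow the patients to be separated. The other is that the main validation must be confined to patients with an untreated baseline. That restriction has its own cost in power and narrows the population to which the result applies, so it is a matter of judgement.

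**What to change.** 1. Reconcile the inclusion criteria, in both the synopsis and section 8.1, with the synopsis paragraph on other therapy and with section 7. State plainly whether a patient who has had anticancer therapy before the baseline scan is eligible. This note takes no view on which treatment rule is right.
2. If such patients are eligible, use the recorded treatment dates to define in section 12.2 a flag for any anticancer therapy before the baseline scan.
3. Include the flag in hypothesis generation and in the Cox model. Report the validation kappa separately by the flag as well as pooled. Name the analysis of patients with an untreated baseline as a pre-specified supporting analysis.

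The cost is wording and one derived variable; no new data are needed. The drawback is smaller strata. With 20% pretreated, the untreated-baseline analysis of a 70-patient group has 56 patients and about 85% power under the assumptions above. The pretreated stratum would have about 14 patients and could only be described.

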**Pilot study**

The first 30 patients will have the study procedures at different time points after start of radiotherapy. Different sequencing of biopsy and imaging procedures will be employed. This is in order to find the shortest interval between start of therapy and imaging to be able to detect differences in functional imaging parameters. The results will be used for establishing the precise schedule for remaining patients. These patients will not be included in the final analyses.

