The concept of metabolomics is the systematic study of the unique chemical fingerprints caused by specific cellular processes, where the analysis is expanded to hundreds to thousands of metabolites (< 1kDa). This can be compared to traditional metabolic studies where only a limited set of molecules is studied. Metabolomics has attracted large interest in recent years, since it has the power and scope to resolve fundamental biological issues that cannot be readily addressed using other approaches. Metabolomics information represents a more complete description of the organism closest to the function or phenotype, but also more complex than explanations based on, e.g. functional genomics, proteomics and transcriptomics. To model the systems biology from genome to function or phenotype (tumour) based on these pieces of information, using parametric methods is not realistic today. However, to analyse the systems biology by non-parametric methods as applied in metabolomics research is fully feasible. Current studies of metabolomics are, however, limited to samples representing the whole system or by invasive methods obtained samples and cannot detect heterogeneities in tumours or even locate the signalling tissue. In order to move the metabolomics from isolated research studies to diagnostic predictive and monitoring systems, there is a need for more powerful data collection and data processing tools. Both PET and MRI have the capability to measure metabolic activity and system vascularity in volume elements of approximately 1-10 mm^3. The molar sensitivity of a PET system is very high, in the order of 10^-15 molar. The combination of the high spatial resolution of the MRI technique and the high sensitivity of the PET system will enable detection of, e.g. therapy-resistant tumour sub-volumes. Sampling of repeated functional images will be an integrated part of the large-scale data sampling. The initial aim of the project will be to determine metabolic fingerprints over time from samples and images, and correlate these to disease, therapy and outcome. Chemometrics and projection-based methods such as Principal Component Analysis (PCA), Partial Least Squares (PLS) and Orthogonal PLS (OPLS) are well-established methods in metabolomics for predictive modelling, powerful data visualization and model interpretation (Holmes & Antti 2002, Trygg, Holmes et al. 2007). However, time trends of a biological system are

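### Tissue is sampled under different rules at baseline and Day 8, so tissue change mixes treatment effect with choice of site, and neither rule nor location need be recorded for analysis

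*Protocol*

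**What the plan says.** Protocol section 7 gives each assessment its own order of procedures.

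- **First assessment:** "Tissue specimens should be obtained as soon as possible before imaging".
- **Second assessment (Day 8 ± 1):** "The biopsy/FNAC should preferably be performed after imaging in order to avoid bleeding or edema blunting the imaging". The same paragraph continues: "It is recommended that the images produced are used as guidance for directing the biopsies at volumes assumed to contain active tumour tissue".
- **Fallback at the second assessment:** if that is not "possible the biopsy/FNAC may be performed before imaging under the condition that the surgeon provides detailed description of the location of the biopsy". The stated purpose of that description is to correct for artefacts near the biopsy, not to match the baseline site.

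The use of the samples is set in section 4.1.2, where the first specific aim is to "Correlate changes in imaging bio-markers to corresponding changes in tissue or blood bio-markers by repeated imaging and biopsies", and in section 12.2: "Changes in imaging parameters and metabolomics patterns will be used for statistical inference".

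Section 9.1.1 limits tumour biopsy and blood sampling to patients in the exploratory part of the study. The Synopsis says of the pilot: "Different sequencing of biopsy and imaging procedures will be employed".

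**The concern.** A within-patient change can be read as a treatment effect only if both measurements sample the tumour in the same way. Here the baseline specimen cannot be directed by the study images, while the Day 8 specimen preferably is, towards tissue presumed active. The difference between the two contains the treatment effect plus whatever separates an image-selected site from one not so selected.

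Two features make this worse for a change-on-change correlation. Guidance is a recommendation with a fallback, so the sampling rule at Day 8 varies between patients. And where guidance is used, the imaging signal itself picks the tissue whose change is then correlated with imaging change, so the two quantities are not obtained independently.

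The protocol's own background implies that site matters. Section 3.1 expects differing responses in subsets of a tumour, and says that current metabolomics on whole-system or invasively obtained samples "cannot detect heterogeneities in tumours or even locate the signalling tissue". At stake is whether the tissue work can explain what the image parameters mean.

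**Working it through.** The plan states no figure on this point, so there is none to reproduce. The check sets the two rules side by side and then illustrates the consequences. All inputs below are assumptions except n = 70, which is the per-group target in section 12.1; the number with paired tissue may be smaller.

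**1. The rules compared**

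| | First assessment | Second assessment |
|---|---|---|
| Order | tissue before imaging | tissue preferably after imaging |
| Use of that session's study images | impossible | recommended, with fallback |
| Site description | not required in section 7 | required only in the fallback, for artefacts |
| Specimen type | biopsy or FNAC | biopsy or FNAC, no match required |

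**2. Mean tissue change with no treatment effect**

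Let the first sample fall at a random site and the second in the top fraction q of the image signal. Let r be the within-tumour correlation between image signal and tissue marker. The false mean change, in within-tumour SD, is r × φ(z)/q, with z the normal quantile at 1 − q.

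- q = 0.50: φ(z)/q = 0.399/0.50 = 0.80. For r = 0.2, 0.4, 0.6 the shift is 0.16, 0.32, 0.48.
- q = 0.25: φ(z)/q = 0.318/0.25 = 1.27. The shift is 0.25, 0.51, 0.76.

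With n = 70 and the SD of a difference taken as √2, the standard error is √(2/70) = 0.169. The chance of a significant change in the direction of the shift is Φ(shift/0.169 − 1.96): 15%, 47%, 81% for q = 0.50 and 32%, 85%, 99% for q = 0.25. If half of the second samples are guided, the shift halves, to between 0.08 and 0.38 SD. With one rule at both sessions it is 0.

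**3. Correlation of tissue change with tumour response**

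A shift identical in every patient would bias the mean and leave a correlation alone, so this needs its own check. Let the active fraction be 0.80 at baseline and fall by D, uniform on 0 to 0.6; Var(D) = 0.6²/12 = 0.03, SD 0.173. The first sample is active (A1 = 1) with probability 0.80. The second (A2) is active with probability 0.80 − D if unguided, or a constant g of 0.80 to 0.95 if guided. The marker in active tissue is L = 1 − cD/0.6, where c is the fall at maximum response. Tissue change is Y = A2·L − A1, plus measurement noise of SD 0.2 per sample (variance 0.08 on the difference) where stated. Entries are the correlation of Y with −D.

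| Marker inside active tissue | Unguided at both | Second sample guided |
|---|---|---|
| no change (c = 0, no noise) | 0.27 | 0 |
| falls by a quarter (c = 0.25, noise) | 0.28 | 0.10 to 0.13 |
| falls fully (c = 1, noise) | 0.38 | 0.39 to 0.48 |

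Worked entries:

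- c = 0, unguided: covariance 0.03; Var(Y) = 0.16 + 0.25 = 0.41; 0.03/(0.173 × 0.640) = 0.27.
- c = 0, guided: A2 has the same probability in every tumour, so the covariance is 0 by construction.
- c = 1, guided, g = 0.95: covariance (0.95/0.6) × 0.03 = 0.0475; Var(A2·L) = 0.95/3 − 0.475² = 0.091; Var(Y) = 0.16 + 0.091 + 0.08 = 0.331; 0.0475/(0.173 × 0.575) = 0.48.

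Two softer versions of the first row, by simulation: with half of second samples guided the correlation is about 0.14; with guidance multiplying the odds of hitting active tissue by 2 to 10 it is 0.25 down to 0.13. Distortion is therefore possible in either direction, and no run gives a negative correlation.

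**The case against.** The strongest reply is that this is minor and partly deliberate. Guidance is only recommended, and aiming at active tumour may mean no more than avoiding necrotic or non-tumour tissue. The baseline sample is not blind either: inclusion criterion 3 in section 8.1 requires a tumour that can be identified radiologically or visually and reached for biopsy. The pilot varies the sequence and sets the later schedule. Addenda 1 to 3 appear by title only, so location recording may exist there. Tissue work is exploratory, and section 5 gives it an explanatory role.

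Much of this stands and limits the point. It does not remove it. A recommendation with a fallback produces mixed sampling modes, which section 7 does not ask anyone to record or separate. The pilot's stated purpose is the shortest interval at which imaging change is detectable, not comparable tissue sampling. If the guidance sentence is read as covering both biopsies, it conflicts with taking the first one before imaging, so section 7 needs reconciling on either reading.

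A reader might go further and infer that guidance drives the imaging-tissue correlation to zero or reverses it, or that the needle is always steered to the least-responding part of the tumour. The documents support neither. The zero in the table is built into its assumption, the last row shows a rise, and section 7 speaks only of tissue presumed active.

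**Conclusion.** The point holds for the tissue part of specific aim 1, in exploratory patients only. As written, section 7 confounds tissue change with a change of sampling rule that differs between patients, and it lets the imaging signal choose the second site.

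The mean tissue change is biased if the marker varies within the tumour with the image signal. The 0.16 to 0.76 SD range rests on assumed r of 0.2 to 0.6 and on every second sample being guided into the most active half or quarter. The correlation can be distorted, but its size and direction depend on how well guidance works and on how the marker moves inside viable tissue. No fixed magnitude and no sign change should be claimed.

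It would also be wrong to conclude that specific aim 1 as a whole fails: blood markers do not depend on biopsy site, and the primary endpoint is unaffected. The matter still deserves correction, because a sampling location or mode that was not recorded cannot be recovered at analysis.

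**What to change.** In section 7 and on the CRF:

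- At both sessions, record sample location (mapped to the co-registered images), specimen type (biopsy or FNAC) and guidance mode (image-guided or not). If an addendum already asks for any of this, refer to it.
- Correlate each sample with the image values of the sub-volume it came from, not with whole-tumour change.
- Analyse tissue change stratified by, or adjusted for, guidance mode, with a sensitivity analysis limited to pairs sampled under the same rule.
- Reconcile the order of biopsy and imaging at the two sessions, and state whether the guidance sentence applies to one or both.

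The cost is one further CRF entry per sample, some image-registration work, and lower precision in the same-rule subset. No extra biopsy is needed. Returning to the same sub-region, or dropping guided samples, is not required: either would carry a price of its own, in samples with little viable tumour or in loss of the mode the protocol prefers.
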